11.44 Overall Objective Status

The overall objective status for an evaluation is determined by combining the patient's status on target lesions, target lymph nodes, non-target lesions, non-target lymph nodes, and new disease as defined in the following tables:

11.441 Objective Status Table for Patients with Measurable Disease

Target Lesions & Target Lymph Nodes	Non-Target Lesions & Non-Target Lymph Nodes	New Sites of Disease	Overall Objective Status
CR	CR	No	CR
CR	Non-CR/Non-PD	No	PR
PR	CR Non-CR/Non-PD	No	PR
CR/PR	Not All Evaluated*	No	PR**
SD	CR Non-CR/Non-PD Not All Evaluated*	No	SD
Not all Evaluated	CR Non-CR/Non-PD Not All Evaluated*	No	Not Evaluated (NE)
PD	Unequivocal PD CR Non-CR/Non-PD Not All Evaluated*	Yes or No	PD
CR/PR/SD/PD/Not all Evaluated	Unequivocal PD	Yes or No	PD
CR/PR/SD/PD/Not all Evaluated	CR Non-CR/Non-PD Not All Evaluated*	Yes	PD

*See Section 11.431

** NOTE: This study uses the protocol RECIST v1.1 template dated 2/16/2011. For data collection and analysis purposes the objective status changed from SD to PR in the MCCC protocol RECIST v1.1 template as of 2/16/2011 and to match RECIST v1.1 requirements.

11.45 Symptomatic Deterioration

Patients with global deterioration of health status requiring discontinuation of treatment without objective evidence of disease progression at that time, and not either related to study treatment or other medical conditions, should be reported as PD due to "symptomatic deterioration." Every effort should be made to document the objective progression even after discontinuation of treatment due to symptomatic deterioration. A patient is classified as having PD due to "symptomatic deterioration" if any of the following occur that are not either related to study treatment or other medical conditions:

- Weight loss >10% of body weight.
- Worsening of tumor-related symptoms.
- Decline in performance status of >1 level on ECOG scale.

12.0 Descriptive Factors

- 12.1 Prior lines of treatment: 0 vs. 1 vs. 2 vs. 3+
- 12.2 Extrahepatic spread of disease: Yes vs. No
- 12.3 Macrovascular invasion: Yes vs. No

13.0 Treatment/Follow-up Decision at Evaluation of Patient

- 13.1 Continuation of treatment

Patients who are CR, PR, or SD will continue treatment per protocol.

- 13.2 Progressive disease (PD)

Patients who develop PD while receiving therapy will go to the survival follow-up phase.

- 13.3 Off protocol treatment

Patients who go off protocol treatment for reasons other than PD will go to the clinical follow-up/observation phase per Section 4.0. Participants will be required to return to the consenting site for follow-up until disease progression, new anti-cancer therapy, death, withdrawal of consent for clinical followup, or a maximum of 18 months from Registration.

- 13.4 Duration of therapy for CR

Patients who achieve a CR will receive a maximum total of 35 cycles (i.e., 2 years). After 35 cycles, they will go to survival follow-up/event monitoring. Subsequent treatment is at the discretion of their attending physician.

- 13.5 Duration of therapy for PR or SD

Patients who are in PR or SD will continue on therapy for a total of 35cycles (i.e., 2 years). After 35 cycles, they will go to survival follow-up/event monitoring. Subsequent treatment is at the discretion of their attending physician.

- 13.6 Ineligible

A patient is deemed *ineligible* if after registration, it is determined that at the time of registration, the patient did not satisfy each and every eligibility criteria for study entry. If the patient received treatment, the patient may continue treatment at the discretion of the physician as long as there are not safety concerns. The patient will continue in the Active Monitoring/Treatment phase of the study, per [Section 4.0](#) of the protocol.

- If the patient never received treatment, on-study material must be submitted. Survival follow-up/event monitoring will be required per [Section 4.0](#) of the protocol.

- 13.7 Major violation

A patient is deemed a *major violation*, if protocol requirements regarding treatment in Cycle 1 of the initial therapy are severely violated that evaluability for primary endpoint is questionable. If the patient received treatment, the patient may continue treatment at the discretion of the physician as long as there are not safety concerns. The patient will continue in the Active Monitoring/Treatment phase of the study, per [Section 4.0](#) of the protocol.

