7.0 Protocol Treatment

7.1 Treatment Schedule

Patients may receive treatment on this trial for up to 2 years until disease progression, unacceptable adverse events, or patient refusal.

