7.11 Treatment medication table – Cycles 1-9

Agent	Dose Level	Route	Day	ReRx
futibatinib	20 mg*	oral	Once daily on Days 1-21	Q3w
pembrolizumab	200 mg	IV	1	Q3w

Cycle length = 21 days ± 3 days

*Investigator may start patients at lower dose (16mg) if clinically indicated (e.g., patient history of diarrhea) after discussion with PI

Once patients have completed Cycle 9, the cycle length can be increased to 6 weeks with imaging every other cycle (~12 weeks).

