7.12 Treatment medication table – Cycles 10 and beyond

Agent	Dose Level	Route	Day	ReRx
futibatinib	20 mg	oral	Once daily on Days 1-42	Q6w
pembrolizumab	400 mg	IV	1	Q6w

Cycle length = 42 days ± 7 days

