7.3 Return to consenting institution

For this protocol, the patient must return to the consenting institution for evaluation at least every 21 days ± 3 days during treatment for first 9 cycles. Beginning with Cycle 10 patients must return at least every 42 days ± 7 days.

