16.5 Operation Characteristics

The probability of declaring that this regimen warrants further studies (i.e., statistical power) under various success proportions can be tabulated as a function of the true success proportion as shown in the following table.

If the true success proportion is:	25%	47%
then the probability of stopping early is:	0.4597	0.0037
and the probability of declaring that the regimen warrants further studies is:	0.0651	0.7923

The operation characteristics were calculated using simulation with 10,000 replications. PFS6 of 25% is generated using Weibul distribution (scale=0.3, shape=0.6667) PFS6 of 47% is generated using Weibul distribution (scale=0.73, shape=0.8850)

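### The 35-cycle limit in Sections 13.4 and 13.5 equals 2 years only on 3-week cycles; with 6-week cycles from Cycle 10 it is 183 weeks, about 3.5 years

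*Combined protocol and SAP*

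**What the plan says.** Section 7.1 sets a calendar limit: "Patients may receive treatment on this trial for up to 2 years until disease progression, unacceptable adverse events, or patient refusal".

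Section 13.4 expresses that limit as a cycle count for complete responders: "Patients who achieve a CR will receive a maximum total of 35 cycles (i.e., 2 years". Section 13.5 does the same for everyone else without progression: "Patients who are in PR or SD will continue on therapy for a total of 35cycles (i.e., 2 years". In both subsections the step that takes the patient off treatment is the count: "After 35 cycles, they will go to survival follow-up/event monitoring".

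Cycle length is not constant. Cycles 1 to 9 are 21 days. After that, Section 7.11 says "Once patients have completed Cycle 9, the cycle length can be increased to 6 weeks". Section 7.12, the dosing table for Cycle 10 onward, gives "Cycle length = 42 days ± 7 days", with pembrolizumab at 400 mg in place of 200 mg. Section 7.3 sets visits to match: "Beginning with Cycle 10 patients must return at least every 42 days ± 7 days". The schema and the test schedule in Section 4.1 also use 42 days from Cycle 10. No section restates the 35-cycle figure for the longer cycle.

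**The concern.** Two years is stated in 7.1, 13.4 and 13.5 and is evidently the intended limit. The 35-cycle figure fits a schedule made up entirely of 3-week cycles and was not converted for the 6-week schedule that the protocol also permits.

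This matters because the count is the instruction that ends treatment. Take a patient in PR on 6-week cycles who has just finished Cycle 22. Under 7.1 treatment is over; under the trigger in 13.5 there are 13 cycles to go. The protocol does not say which governs. Two investigators could follow the text and stop similar patients 1.5 years apart, and either could be recorded as deviating. What is at stake is maximum exposure to an investigational combination, and the late safety experience in a few long-term patients.

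**Working it through.** **Inputs**
- Limit: 35 cycles, equated with 2 years (13.4, 13.5); 2 years (7.1).
- Cycle length: 3 weeks for Cycles 1–9 (7.11); 6 weeks from Cycle 10 if the switch is made (7.11, 7.12).
- Windows: ±3 days on 21-day cycles, ±7 days on 42-day cycles.
- 2 years = 2 × 365.25 / 7 = 104.4 weeks.

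**1. Reproducing the plan's figure.** All cycles 3 weeks: 35 × 3 = 105 weeks = 2.01 years. The stated equivalence holds on this schedule.

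**2. The same count on 6-week cycles from Cycle 10.** Duration = 9 × 3 + (35 − 9) × 6 = 27 + 156 = 183 weeks = 3.51 years. The excess is 183 − 105 = 78 weeks, about 1.5 years. With every cycle at the edge of its window, the range is (9 × 18 + 26 × 35) = 1,072 days to (9 × 24 + 26 × 49) = 1,490 days, or 2.93 to 4.08 years. Even the short end is well past 2 years.

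**3. Where 2 years falls.** Cycle number = 9 + (104.4 − 27) / 6 = 21.9.

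| End of cycle | Weeks | Years |
|---|---|---|
| 21 | 27 + 12 × 6 = 99 | 1.90 |
| 22 | 27 + 13 × 6 = 105 | 2.01 |
| 23 | 27 + 14 × 6 = 111 | 2.13 |

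Cycle 22 therefore ends in the same week as the 35th three-week cycle.

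**4. Cross-check on pembrolizumab dose.** Thirty-five 3-week cycles: 35 × 200 = 7,000 mg. At Cycle 22 on the mixed schedule: 9 × 200 + 13 × 400 = 7,000 mg. At Cycle 35 on the mixed schedule: 9 × 200 + 26 × 400 = 12,200 mg. So 22 is the cycle number equivalent to 35.

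**5. Later switch.** If 6-week cycles start after Cycle 20: 20 × 3 + 15 × 6 = 150 weeks = 2.87 years. If the patient never switches, there is no excess.

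**6. How many patients.** Section 16.5 gives Weibull parameters for PFS: scale 0.3 and shape 0.6667 under the null and, for the alternative, "PFS6 of 47% is generated using Weibul distribution (scale=0.73, shape=0.8850". The time unit is not stated; I assume years, with S(t) = exp[−(t/scale)^shape]. At 0.5 years this gives 24.5% and 48.9%, and at 27 weeks 23.7% and 47.8%, against the stated 25% and 47%, so the reading is reasonable.

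| Time | Null S(t) | × 22 | Alternative S(t) | × 22 |
|---|---|---|---|---|
| 2 years | 0.029 | 0.64 | 0.087 | 1.92 |
| 3.51 years | 0.006 | 0.13 | 0.018 | 0.40 |

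**The case against.** The best case for the text is that the intended limit is clear. Two years appears in 7.1 and again beside the cycle count in both 13.4 and 13.5, so a reader reaches 3.5 years only by ignoring the words next to the number. The switch to 6-week cycles is worded as permitted, so the mismatch is conditional. The expected number of patients is below two at 2 years and below one half at 3.51 years. Those figures extrapolate curves set to match a 6-month rate, and progression-free patients may already have stopped for toxicity or refusal. Adverse events are assessed at every cycle and collected until at least 30 days after the last dose, so extra exposure would not go unobserved.

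Most of this stands as a limit on the size of the problem. It does not remove the conflict: the sentence that stops treatment uses the count alone, and it fails on the only cycle length tabulated for Cycle 10 onward.

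A second objection is that calendar time could shorten treatment for a 3-week patient with delays, since 35 cycles at the window edges run from 35 × 18 = 630 to 35 × 24 = 840 days (1.7 to 2.3 years). That is true, and it means the count and the calendar coincide only nominally even on 3-week cycles. But 7.1 already limits every patient to 2 years, so the rewording imposes nothing new.

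It is also fair to note that Section 1.6 describes treatment until progression or unacceptable toxicity with no time limit. That gives no help in deciding between the two limits.

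**Conclusion.** The concern holds; the cycle equivalence in 13.4 and 13.5 is wrong as written for any patient on 6-week cycles. The largest discrepancy is 183 against 105 weeks (3.51 against 2.01 years), for a switch at Cycle 10. It shrinks with a later switch and is nominally nil if 3-week cycles are kept. The durations rest only on the protocol's nominal cycle lengths.

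The patient numbers (about 0.6 to 1.9 of 22 progression-free at 2 years) rest on reading the Weibull scale in years and extrapolating well past 6 months. They are an upper guide to the number still on drug, because they ignore other reasons for stopping.

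The primary endpoint is fixed at 27 weeks, before any patient could reach either limit, so PFS6, the sample size and the error rates do not change. This should be corrected because it is a stopping rule for an investigational combination that contradicts itself on a permitted schedule. It does not threaten the trial's main conclusion.

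**What to change.** Leave Section 7.1 as it is. In 13.4 and 13.5, replace both the 35-cycle limit and the 35-cycle trigger with calendar time, for example:

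*Treatment continues for no more than 2 years from Cycle 1 Day 1 (nominally 35 cycles if all are 3-week cycles, or about 22 cycles if 6-week cycles start at Cycle 10). At 2 years the patient moves to survival follow-up.*

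The start date has to be named because neither 7.1 nor Section 13 gives one; Cycle 1 Day 1 is the natural choice for a limit on exposure.

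The cost is a wording correction in two subsections. It brings 3-week patients with accumulated delays into line with the limit that 7.1 already sets, and it leaves the dosing schedule, visits, primary analysis and sample size unchanged.

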13.8 Cancel

A patient is deemed a *cancel* if he/she is removed from the study for any reason before any study treatment is given. On-study material and the End of Active Treatment/Cancel Notification Form must be submitted. No further data submission is necessary.

13.9a Subsequent Anti-Cancer Therapy Status

The investigator or qualified designee will review all new anti-neoplastic therapy initiated after the last dose of trial treatment. If a participant initiates a new anti-cancer therapy within 30 days after the last dose of trial treatment, the 30-day Safety Follow-up visit must occur before the first dose of the new therapy. Once new anti-cancer therapy has been initiated the participant will move into survival follow-up/event monitoring per [Section 4.0](#).

14.0 Body Fluid Biospecimens

14.1 Summary Table of Research Blood and Body Fluid Specimens to Be Collected for this Protocol

Research (Section for more information)	Specimen Purpose (check all that apply)	Mandatory or Optional	Blood or Body Fluid being Collected	Type of Collection Tube (color of tube top)	Volume to collect per tube (# of tubes to be collected)	Baseline prior to Cycle 1, Day 1	Prior to Cycle 4 Day 1	End of treatment	Process at site? (Yes or No)	Temperature Conditions for Storage /Shipping
cfDNA based studies (Section 14.2 and 14.3)	 Correlative	Mandatory	Whole blood for platelet poor plasma	Streck cfDNA BCT	10 mL (2)	X	X	X	Yes	Frozen
Immune profiling	 Correlative	Mandatory	Whole blood	EDTA tube (purple top)	10 mL (1)	X	X	X	No	Ambient - Send immediately to [REDACTED]
Banking	 Banking	Mandatory	Whole blood for DNA, buffy coat and plasma	EDTA tube (purple top)	10 mL (1)	X	X	X	Yes	Frozen
Banking	 Banking	Mandatory	Whole blood for DNA	EDTA tube (purple top)	4 mL (1)	X			Yes	Frozen

14.2 Collection and Processing

14.21 Sample collection should be restricted to Monday – Thursday. However, if the subject can only be seen on a Friday, please contact the laboratory of [REDACTED] and the Biospecimen Accessioning and Processing (BAP) Service Center for additional instructions (see [protocol resource](#) pages for contact information).

14.22 Specimen tube(s) must be labeled with the protocol number, study patient ID number, and the time and date of the blood draw.

14.23 Blood/blood products must be collected and shipped according to specific instructions provided in the kit and the table above.

14.3 Shipping (AZ/FL only)

14.31 Verify that ALL sections of the Blood Specimen Submission Form (see Forms Packet), BAP Requisition Form (provided in kit), and specimen collection labels are completed and filled in correctly. Enter information from the Blood Specimen Submission Form into the remote data entry system within 7 days after specimen collection (see Forms Packet).

14.32 Specimens collected in the Streck cfDNA BCT and AccuCyte tubes should be shipped at ambient temperature on the same day they are drawn.

14.33 Specimens collected in EDTA tubes should be processed for DNA from whole blood, a buffy coat back up and plasma aliquots then stored frozen.
NOTE: DNA extraction may be done at site where it's collected.

14.34 Samples should be shipped to BAP Freezer Mondays – Thursdays according to kit instructions. Samples should not be sent on weekends or just prior to federal holidays. (If samples can only be shipped on Fridays, please contact the Biospecimen Resource Manager for additional instructions.)

14.4 Processing

NOTE: BAP Shared Resource will process the specimens.

14.41 Double spun, platelet poor plasma will be derived from the Streck cfDNA BCT tubes using established laboratory processes, and stored at $\leq -65^{\circ}\text{C}$ by BAP.

14.42 DNA will be extracted from whole blood, and white blood cells and plasma will be derived from remaining blood from the EDTA tubes, divided into aliquots, and stored at $\leq -65^{\circ}\text{C}$ by BAP according to patient consent information.

14.43 One EDTA should be delivered immediately to [REDACTED] Immunology, [name].

14.44 As part of ongoing research at the Mayo Clinic, we will retain residual whole blood, white blood cells, DNA, and plasma for future research studies, according to patient consent information. Samples will be stored until specific analyses are identified and may be used for exploratory biomarker analyses, validation

studies, or potential diagnostic development. As protocols are developed, they will be presented for IRB review and approval.

14.5 Methodology

14.51 cfDNA

10 mL whole blood samples will be collected in Streck cfDNA BCT tubes. These specimens will be shipped immediately at ambient temperature to Mayo Clinic Rochester and then processed to aliquots of platelet poor plasma within 7 days of collection using standard protocols. Samples will be stored until we are ready for DNA extraction and mutational analysis. Mutation analysis will be performed on the baseline cfDNA samples. Selected mutations identified at baseline will be verified and quantified in all cfDNA samples using ultrasensitive digital droplet PCR based assays.

15.0 Drug Information

15.1 Futibatinib (TAS-120)

15.11 Background

Futibatinib is a novel and selective small molecule irreversible, covalent kinase inhibitor of fibroblast growth factor receptor (*FGFR*) 1–4. Futibatinib equally inhibited all 4 subtypes of FGFR and showed high selectivity for FGFR when tested against a panel of 296 kinases. Futibatinib was highly active against cancer cell lines with FGFR gene abnormalities including cancer cell lines that acquired resistance to other adenosine triphosphate (ATP) competitive FGFR tyrosine kinase inhibitors (TKIs).

15.12 Formulation

Futibatinib (TAS-120) is available as 4 mg tablets in dose pak blister cards containing 28 tablets/card. The 4 mg tablet is a round, white or light yellow, film coated tablet.

15.13 Preparation and storage

Store at room temperature between 15-30° Celsius.

15.14 Administration

Futibatinib is taken orally at a starting dose of 20 mg daily at the same time each day. Futibatinib may be taken with or without food.

In the event of a dosing delay up to 12 hours after the scheduled dosing time, the patient should still take that day's dose. If the dosing delay continues for >12 hours after the scheduled dosing time, or if the patient vomits after a dose, the patient should skip dosing for that day and not make up for it the following day.

15.15 Pharmacokinetic information

PK parameters of futibatinib at a dose of 20 mg daily (Study TAS-120-101):

C_{max} (CV%): 50%

T_{max} : 2 hours

AUC_{last} : 790 ng*hr/mL

$T_{1/2}$: 3 hours

Protein Binding: 95%

Metabolism: The primary cytochrome P450 enzyme is CYP3A
(minor: glutathione S-transferase [GST])

15.16 Potential drug interactions

To date, three clinical drug-drug interaction studies and one PK model analysis have been conducted in humans. These studies have shown that strong inhibitors or inducers of CYP3A and dual P-gp have potential clinical drug-drug interactions with futibatinib. Such inhibitors may increase futibatinib exposure and thus increase the incidence and severity of AEs associated with futibatinib. And such inducers may decrease futibatinib exposure and thus reduce the efficacy of futibatinib.

Effect of Other Drugs on Futibatinib

Futibatinib is a substrate of CYP3A and P-gp.

Dual P-gp and Strong CYP3A Inhibitors: Avoid concomitant use of drugs that are dual P-gp and strong CYP3A inhibitors with futibatinib. Concomitant use of drugs that are dual P-gp and strong CYP3A inhibitors with futibatinib may

increase futibatinib exposure, which may increase the incidence and severity of adverse reactions.

Dual P-gp and Strong CYP3A Inducers:

Avoid concomitant use of dual P-gp and strong CYP3A inducers with futibatinib. Concomitant use of drugs that are dual P-gp and strongCYP3A inducers may decrease futibatinib exposure, which may reduce the efficacy of futibatinib.

Effect of Futibatinib on Other Drugs

Futibatinib is an inhibitor of P-gp and BCRP.

P-gp or BCRP Substrates:

Consider more frequent monitoring for adverse reactions associated with concomitantly administered drugs that are sensitive substrates of P-gp or BCRP and reduce the dose of these drugs per their Prescribing Information.

Futibatinib may increase exposure of drugs that are substrates of P-gp or BCRP.

15.17 Known potential adverse events

Reported from daily dosing schedule (Study 10059010)

Most common adverse events ($\geq 15\%$):

Hyperphosphatemia, decreased appetite, constipation, diarrhea, nausea, vomiting, ALT and AST increased, anemia, stomatitis

Reported from daily dosing schedule (Study TPU-TAS-120-101)

Most common adverse events ($\geq 15\%$):

Hyperphosphatemia, diarrhea, constipation, nausea, dry mouth, ALT and AST increased, fatigue, vomiting, alopecia, decreased appetite, anemia, stomatitis, abdominal pain, dry skin, palmar-plantar erythrodysesthesia syndrome, blood creatinine increased, hypercalcemia, back pain, dry eye, pyrexia, arthralgia, dysgeusia, urinary tract infection, weight decreased, nail disorder, hyponatremia, onycholysis, onychomadesis

Reported from daily dosing schedule (Study TAS-120-201)

Most common adverse events ($\geq 15\%$):

Hyperphosphatemia, constipation, ALT and AST increased, decreased appetite, diarrhea, dry mouth, nausea, alopecia, fatigue, anemia, asthenia, rash, vomiting

15.18 Drug procurement:

Futibatinib will be supplied by the Taiho Oncology, Inc.

Outdated or remaining drug is to be destroyed on-site per procedures in place at each institution.

15.19 Nursing guidelines

15.191 Assess patient's concomitant medications as there are many drug-drug interactions.

15.192 Gastrointestinal side effects are common, including diarrhea, constipation, nausea, vomiting and abdominal pain. Treat symptomatically and monitor for effectiveness.

15.193 Monitor LFTs.

15.194 Patients may experience dermatologic side effects including, dry skin, and palmar-plantar erythrodysesthesia (PPE aka hand-foot syndrome). Instruct patients to report any skin changes to the study team. For PPE, encourage frequent moisturizing of the hands and feet, with a urea based cream if possible.

- 15.195 Patients may experience pyrexia. Instruct patients to report fever to the study team.
- 15.196 Instruct patients to report all side effects to the study team.
- 15.197 Eye problems are common. Instruct patient to report any changes in their eyes or vision to the study team.

15.2 **Pembrolizumab (MK-3475, SCH 900475, Keytruda®)**

